2.5 DATA HANDLING CONVENTIONS

2.5.1 General conventions

The following formulas will be used for computation of parameters.

Demographic formulas

Age is calculated as:

Integer part of (informed consent date -birth date)/365.25

Age of asthma onset is calculated as:

Integer part of (asthma onset date - birth date)/365.25

- Time since first diagnosis of asthma (years) is calculated as:
 - (Year of randomization Year of first diagnosis of asthma) + (month of randomization month of first diagnosis of asthma)/12
- Time since cessation of smoking is calculated as:
- (Year of randomization Year of cessation)×12 + (month of randomization -month of cessation)
- Time since last asthma exacerbation (months) is calculated as:

 $(Year of randomization - Year of last asthma exacerbation) \times 12 + (month of randomization - month of last asthma exacerbation)$

BMI is calculated as:

Weight in kg / (height² in meters)

Smoking quantity (pack-year) is calculated as following: Number of pack-year= (packs smoked per day) × (years as a smoker)

Renal function formulas

For patients \geq 18 years old, creatinine clearance (CLcr) value will be derived using the equation of Cockroft and Gault:

CLcr (ml/min) = $(140 - age) \times \text{weight} (\text{kg}) \times (1 - 0.15 \times \text{sex} (0-\text{M}, 1-\text{F}))/(0.814 \times \text{creatinine})$

 $(\mu mol/l))$

CLcr will be calculated using the last weight measurement on or before the creatinine measurement was assessed and age at the lab sampling date. Here age is calculated as following:

Age = integer part of (lab sampling date - birth date)/365.25

For patients < 18 years old, CLcr value will be derived using the equation of GFR Bedside Schwartz

GFR $(mL/min/1.73 m2) = k \times height (cm) / sCr (mg/dL)],$

Where the coefficient k=0.65 for adolescent male patients, or k=0.55 for adolescent female patients.

2.5.2 Data handling conventions for efficacy variables

OCS dose handling conventions

The percentage reduction of OCS dose at the visits will be calculated as (optimized OCS dose at baseline – OCS dose at the visit)/optimized OCS dose at baseline \times 100%. A negative percent reduction value is possible if at any visit the prescribed dose is higher than the baseline.

Calculation of salbutamol/albuterol or levosalbutamol/levalbuterol puffs/day

A diary day is defined as the period beginning with an Evening diary, and ending with the following day's Morning Diary. The number of salbutamol/albuterol or levosalbutamol/levalbuterol puffs per day is the sum of number of puffs recorded in one diary day

including the evening diary and the following day's morning diary. If one of the values is missing for a diary day, then the data for the diary day is considered missing.

Periodical average of daily efficacy endpoints at designated study days

For the daily efficacy endpoints, the time period used to calculate the periodical average at each designated study time point is summarized in Table 7. Randomization day is used as the reference day (Day 1).

Time point	Morning PEF, asthma symptom score, number of awakenings	Evening PEF, asthma symptom score	Number of puffs/day of salbutamol/albuterol or levosalbutamol/levalbuterol for symptom relief
Week 2	Diary day 2-15	Diary day 1-14	Diary day 1-14
Week 4	Diary day 16-29	Diary day 15-28	Diary day 15-28
Week 6	Diary day 30-43	Diary day 29-42	Diary day 29-42
Week 8	Diary day 44-57	Diary day 43-56	Diary day 43-56
Week 12	Diary day 58-85	Diary day 57-84	Diary day 57-84
Week 16	Diary day 86-113	Diary day 85-112	Diary day 85-112
Week 20	Diary day 114-141	Diary day 113-140	Diary day 113-140
Week 24	Diary day 142-169	Diary day 141-168	Diary day 141-168
Week 28	Diary day 170-197	Diary day 169-196	Diary day 169-196
Week 32	Diary day 198-225	Diary day 197-224	Diary day 197-224
Week 36	Diary day 226-253	Diary day 225-252	Diary day 225-252

Table 7 - Periodical average of daily efficacy assessment

example, diary day 1 includes the evening dairy on day 1 and the morning dairy on day 2.

2.5.3 Missing data

For categorical variables, patients with missing data are not included in calculations of percentages unless otherwise specified. When relevant, the number of patients with missing data is presented.

Handling of missing answer to the 7^{th} question in ACQ-7

If the score is missing from the site report, the FEV1 % predicted value from spirometry test will be used to derive the 7th score. Only the spirometry performed on the same day when ACQ-7 is evaluated will be used. And if there are multiple FEV1% predicted values available on the same day, the lowest one will be used to score the 7^{th} item. If the score of the 7^{th} question is still missing but the questionnaire is complete at the prior visit, the missing score for the 7th question

will be imputed as: (score of the 7th question at the prior visit) \times (sum of scores of the first six questions at the current visit) / (sum of scores of the first six questions at the prior visit). If the questionnaire from the prior visit is not complete either or if the ACQ-7 score at the prior visit is 0, which makes it infeasible to implement the algorithm, the missing score will be imputed as the average of the other six questions at the current visit. If scores of the first six questions are missing, then the ACQ-7 score for the current visit will be missing.

Handling of computation of treatment duration if investigational medicinal product end of treatment date is missing

For the calculation of the treatment duration, the date of the last dose of IMP is equal to the date of last administration reported on the Investigational Product Administration report form page. If this date is missing, the exposure duration should be left as missing.

The last dose intake should be clearly identified in the case report form and should not be approximated by the last returned package date.

Handling of medication missing/partial dates

No imputation of medication start/end dates or times will be performed. If a medication date or time is missing or partially missing and it cannot be determined whether it was taken prior or concomitantly, it will be considered as a prior and a concomitant medication.

Handling of adverse events with missing or partial date/time of onset

Missing or partial adverse event onset dates and times will be imputed so that if the partial adverse event onset date/time information does not indicate that the adverse event started prior to treatment or after the treatment-emergent adverse event period, the adverse event will be classified as treatment-emergent. No imputation of adverse event end dates/times will be performed. These data imputations are for categorization purpose only and will not be used in listings. No imputation is planned for date/time of adverse event resolution.

Handling of adverse events when date and time of first investigational medicinal product administration is missing

When the date and time of the first IMP administration is missing, all adverse events that occurred on or after the day of randomization should be considered as treatment-emergent adverse events. The exposure duration should be kept as missing.

The last dose intake should be clearly identified in the case report form and should not be approximated by the last returned package date.

Handling of missing assessment of relationship of adverse events to investigational medicinal product

If the assessment of the relationship to IMP is missing, then the relationship to IMP has to be assumed and the adverse event considered as such in the frequency tables of possibly related adverse events, but no imputation should be done at the data level.

Handling of missing severity of adverse events

If the severity is missing for 1 of the treatment-emergent occurrences of an adverse event, the maximal severity on the remaining occurrences will be considered. If the severity is missing for all the occurrences, a "missing" category will be added in the summary table.

Handling of potentially clinically significant abnormalities

If a patient has a missing baseline he will be grouped in the category "normal/missing at baseline."

For PCSAs with 2 conditions, one based on a change from baseline value or a normal range and the other on a threshold value, with the first condition being missing, the PCSA will be based only on the second condition.

For a PCSA defined on a threshold and/or a normal range, this PCSA will be derived using this threshold if the normal range is missing; eg, for eosinophils the PCSA is > 0.5 GIGA/L or >ULN if ULN ≥ 0.5 GIGA/L. When ULN is missing, the value 0.5 should be used.

Measurements flagged as invalid by the laboratory will not be summarized or taken into account in the computation of PCSA values.

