The ACQ-5 is a 5-item questionnaire, which has been developed as a measure of subjects' asthma control that can be quickly and easily completed in clinical practice (4). The questions are designed to be self-completed by the subject. The 5 questions enquire about the frequency and/or severity of symptoms (nocturnal awakening on waking in the morning, activity limitation, shortness of breath, and wheezing). The response options for all these questions consist of a 0 (no

Statistical Analysis Plan SAR231893-EFC13691 - dupilumab 18-May-2017 Version number: 1

impairment/limitation) to 6 (total impairment/limitation) scale (Appendix B). The ACQ-5 score is a mean of the values recorded for the individual questions. On the 7-point scale of the ACQ-5, a change or difference in score of 0.5 at patient level is the smallest change that can be considered clinically important, corresponding to the Minimal Clinically Important Difference (MCID) defined by the developer.

Throughout the study subjects should complete the ACQ-5 on a weekly basis using their eDiary. The results from the ACQ-5 will be used as a part of the assessment to determine subject eligibility for OCS dose adjustment. If the ACQ-5 is completed through the eDiary while the subject is at a scheduled in-clinic visit, it is recommended that the ACQ-5 be administered at the same time during the visit.

Based on the eDiary device design, each question needs to be completed otherwise a patient cannot proceed to submit his/her response to the entire ACQ-5 questionnaire. Therefore, no partial missing data is expected.

Asthma Control Quesionnaire-7 question version

The ACQ-7 consists of 7 questions. The first 5 questions assess the most common asthma symptoms: 1. frequency in past week awoken by asthma during the night, 2. severity of asthma symptoms in the morning, 3. limitation of daily activities due to asthma, 4. shortness of breath due to asthma and 5. wheeze, plus 6. short-acting bronchodilator use and 7. FEV₁ (pre-bronchodilator use, % and % predicted use). Patients are asked to recall how their asthma has been during the previous week and to respond to the symptom questions on a 7-point scale (0=no impairment, 6= maximum impairment; Appendix C).

Clinic staff scores the FEV₁% predicted on a 7-point scale.

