A global score is calculated: the questions are equally weighted and the ACQ-7 score is the mean of the 7 questions and, therefore, between 0 (totally controlled) and 6 (severely uncontrolled). Higher score indicates lower asthma control.

The answer to the first 5 questions will be used to calculate an ACQ-5 score for the analysis of the ACQ-5 endpoint.

2.1.3.2.2.2 Patient Reported Outcomes (Health-related Quality of Life/health economic variables/other endpoints)

Patients should complete PROs before undergoing spirometry testing.

For all the questionnaires, similar to the ACQ-5, each question of any questionnaire needs to be completed otherwise a patient cannot proceed to submit his/her response to the entire questionnaire on the ediary device. Therefore, no partial missing data is expected.

2.1.3.2.2.2.1 Asthma Quality of Life Questionnaire

The AQLQ was designed as a self-administered PRO to measure the functional impairments that are most troublesome to patients as a result of their asthma (see Appendix D). The instrument is comprised of 32 items, each rated on a 7-point Likert scale (from 1 to 7). The AQLQ has 4 domains. The domains and the number of items in each domain are as follows:

- Symptoms (12 items)
- Activity limitation (11 items)
- Emotional function (5 items)
- Environmental Stimuli (4 items)

A global score is calculated as the mean of all the 32 items ranging from 1 to 7 and a score by domain is the mean of items in each domain. Higher scores indicate better quality of life.

2.1.3.2.2.2.2 SNOT-22

The SNOT-22 is a validated questionnaire to assess the impact of chronic rhinosinusitis on health related quality of life (see Appendix E). The SNOT-22 has 22 items, 5 domains and a global score. The 5 domains include:

- Nasal (range 0-30)
- Ear (range 0-15)
- Sleep (0-20)
- General and practical (0-30)
- Emotional (0-15)

The range of the global score is 0-110. Lower scores indicate less impact. The recall period of the assessment is within the past 2 weeks.

2.1.3.2.2.2.3 Hospital Anxiety and Depression Scale

The HADS is a general scale used to detect states of anxiety and depression and has been validated in patients with asthma (see Appendix F). The instrument is comprised of 14 items: 7 items each related to anxiety and depression. Each item on the questionnaire is scored from 0-3; with a score for either anxiety or depression ranging between 0 and 21.

2.1.3.2.2.2.4 EQ-5D-5L

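### The SAP's rule for a missing ACQ-7 item 7 has a fallback that misses the zero-denominator case and no upper bound, so read literally it can give undefined or out-of-range scores; the reach is small.

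*SAP*

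**What the plan says.** SAP 2.5.3 handles a missing seventh ACQ-7 item (FEV1 % predicted, scored by clinic staff) in three steps.

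1. If the site's score is absent, it is derived from FEV1 % predicted measured by spirometry on the same day.
2. If item 7 is "still missing but the questionnaire is complete at the prior visit", it is imputed as the prior item 7 score times the current sum of items 1-6, divided by the "sum of scores of the first six questions at the prior visit".
3. If the prior questionnaire is also incomplete, "or if the ACQ-7 score at the prior visit is 0, which makes it infeasible to implement the algorithm", then "the missing score will be imputed as the average of the other six questions at the current visit".

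If items 1-6 are missing, the ACQ-7 score is missing.

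The scale is set out in SAP 2.1.3.2.2, under Asthma Control Questionnaire. Patients answer on a "7-point scale (0=no impairment, 6= maximum impairment" scale, staff score FEV1 % "predicted on a 7-point scale", and "the ACQ-7 score is the mean of the 7 questions and, therefore, between 0 (totally controlled) and 6 (severely uncontrolled"). No cap, truncation or other limit on the imputed item is given.

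**The concern.** The SAP says the fallback is for cases where the ratio cannot be computed. The ratio cannot be computed when its denominator, the prior sum of items 1-6, is 0. The written trigger is a prior ACQ-7 score of 0, which also requires item 7 to be 0. Item 7 comes from spirometry and not from the patient's answers, so the two conditions can differ.

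Separately, a ratio of two sums has no natural ceiling, while an item score does. A programmer following the text would get a missing value, an error or an impossible score, or would have to invent a rule after the data are in hand. At stake is the integrity of a prespecified derivation, not a treatment comparison.

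**Working it through.** **Inputs.** Let p be the prior item 7 (0 to 6), P the prior sum of items 1-6 (0 to 36) and C the current sum of items 1-6 (0 to 36). The formula, trigger and fallback are from SAP 2.5.3. The scale is from SAP 2.1.3.2.2.

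**The plan's own range.** For a complete questionnaire, the mean of seven items scored 0 to 6 runs from 0/7 = 0 to 42/7 = 6. The stated range is reproduced, and it requires every item, including item 7, to lie in 0 to 6.

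**Trigger against denominator.**
- Prior ACQ-7 = (P + p)/7. This is 0 only if P = 0 and p = 0.
- Imputed item 7 = p × C / P. This is undefined whenever P = 0.
- With P = 0 and p from 1 to 6, prior ACQ-7 runs from 1/7 = 0.14 to 6/7 = 0.86. The prior questionnaire is complete and the score is not 0, so the fallback is not triggered and the formula divides by 0.

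**No upper bound.** The imputed item exceeds 6 whenever C/P > 6/p. The resulting total is (C + pC/P)/7 = (C/P) × (P + p)/7, which is the prior ACQ-7 multiplied by C/P.

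| p | P | C | Prior ACQ-7 | Imputed item 7 | ACQ-7 | ACQ-7 if item capped at 6 |
|---|---|---|---|---|---|---|
| 5 | 6 | 12 | 11/7 = 1.57 | 5 × 12/6 = 10 | 22/7 = 3.14 | 18/7 = 2.57 |
| 4 | 3 | 24 | 7/7 = 1.0 | 4 × 24/3 = 32 | 56/7 = 8.0 | 30/7 = 4.29 |

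The first record has an impossible item inside a total that still looks valid. The second has a total outside the stated range.

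**All combinations.** There are 7 × 37 × 37 = 9,583 combinations of p, P and C. Applying the rule literally:
- 222 are undefined (6 values of p × 37 values of C, with P = 0);
- 2,178 give an item 7 above 6;
- 904 of those also give an ACQ-7 total above 6.

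These counts show what the rule permits. They are not frequencies expected in patients.

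**Where the values go.**
- ACQ-7 has a by-visit window in SAP Table 9 (section 2.5.4).
- It is not among the efficacy endpoints in SAP 2.1.3.2.2, the repeated-measures analyses in 2.4.4.4.3 or the testing hierarchy in 2.4.4.3.
- The analysed score is ACQ-5, built from the first five items, so item 7 does not enter it.
- SAP 2.1.1 lists ACQ-7 as a baseline characteristic, but the ratio step should not reach it. The protocol schedules ACQ-5 before randomization and at Visit 3 (section 10.1.2.1), and ACQ-7 first appears at Visit 4 (10.1.2.2.1). A baseline ACQ-7 would therefore have no complete prior ACQ-7, and the in-range fallback would apply.

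**The case against.** The strongest reply is that the intent is plain and the reach close to nil. The SAP's own reason for the fallback is infeasibility of the formula, so a sensible programmer would apply it to any zero denominator. The step is a third resort: spirometry and the ACQ are scheduled at the same post-randomization clinic visits, and same-day FEV1 % predicted is used first. No named post-baseline analysis uses ACQ-7.

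Most of this stands and sets the size of the point. It does not remove it. The reply on intent covers only the zero denominator. Nothing in the text signals an intended ceiling on the imputed item.

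A reader might also infer more than the documents support:

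- **How often it happens.** Any percentage of affected records would need item distributions and visit-to-visit correlations that the documents do not give.
- **A particular item 7 score from the entry criterion of FEV1 below 80% predicted.** The documents supplied do not show the bands that map FEV1 to item 7. The algebra needs only a non-zero prior item 7.
- **An error larger than the 0.5 minimal important difference.** No planned estimate uses these ACQ-7 values, so that threshold has nothing to be compared with.
- **That setting item 7 to 0 when the current six items are all 0 is a further error.** With a non-zero prior sum, that value is defined and in range, and the fallback would give the same. Preferring another imputation there is a matter of judgement.

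**Conclusion.** The rule is wrong as written, in two narrow respects. The fallback condition does not match the condition that makes the formula fail, and the imputed item has no upper bound. Applied literally, the rule is undefined for a prior record with items 1-6 all 0 and item 7 between 1 and 6. It can also give an item above 6 and, less often among the possible combinations, a total above 6. It does not always do so: many imputed values are valid.

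The conclusion rests only on the literal text of SAP 2.5.3 and the 0-6 scale in SAP 2.1.3.2.2, with no assumption about patient data. The consequence is limited to by-visit ACQ-7 values at visits where both the site score and same-day spirometry are missing. A reader might take this as casting doubt on the trial's asthma-control results. The documents do not support that, because ACQ-5 and every endpoint in the testing hierarchy are unaffected. This is a minor specification error worth correcting.

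**What to change.** In SAP 2.5.3, make two edits:

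1. Replace the second fallback condition, a prior ACQ-7 score of 0, with a prior sum of the first six item scores equal to 0.
2. Add that the imputed item 7 is restricted to the range 0 to 6.

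With both changes, all 9,583 combinations are defined and every ACQ-7 score lies between 0 and 6. For example, with P = 0, any non-zero p and C = 6, the fallback gives item 7 = 6/6 = 1.0 and ACQ-7 = (6 + 1)/7 = 1.0.

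The cost is about one sentence of SAP text and a line or so of code. No tested endpoint changes. The documents do not say whether the ratio comes from the instrument's own scoring instructions. The edits leave the ratio in place and alter only results that are undefined or cannot exist on the scale.

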2.5.4 Windows for time points

For the safety assessments, the reference date for the derivation of relative days of events or findings will be the date of first IMP administration. Selected safety variables will be summarized by the analysis window define in Table 8 for the by visit descriptive analysis. All available values from central lab will be assigned to the appropriate visit window. In the event of multiple measurements of the same test in the same window, the one closest to the targeted visit date will be used for the by-visit summary. If they are at the same distance to the target day, the latest one will be used. For procedures planned on Visit 3, if it is done on the same date as the first IMP injection but the performance time is missing, it will belong to Visit 3 time window.

	Time windows for					
Visit	Target Day	Vital signs	Clinical lab testing, Urine pregnancy test	Serum pregnancy test	ECG, Urinalysis, Serum immunoglobulins	Hepatitis screen, HIV screen, ANA and Anti-ds DNA antibogy
Visit 1 (Week -8 to -3)	-56 to - 21			1-		1-
Visit 3 (Week 0)	1	1-	1-		1-	
Visit 4 (Week 2)	15	1+-21				
Visit 5 (Week 4)	29	22-35	1+-42			
Visit 6 (Week 6)	43	36-49				
Visit 7 (Week 8)	57	50-70	43-70			
Visit 8 (Week 12)	85	71-98	71-98		1+-126	
Visit 9 (Week 16)	113	99-126	99-126			
Visit 10 (Week 20)	141	127-154	127-154			1+
Visit 11 (Week 24)	169	155-182	155-210		127-210	
Visit 12 (Week 28)	197	183-210				
Visit 13 (Week 32)	225	211-238				
Visit 14 (Week 36)	253	>238	>210		>210	
1-: up to 1 st dose dat	te/time; 1+: at	fter 1 st dose d	ate/time			

Table 8 – Time window for safety endpoints

For the OCS dose used for efficacy assessment, the baseline dose and the final dose at Week 24/Visit 11 are recorded in the corresponding CRF pages. OCS doses at Visits 5, 7, 8, 9, and 10 during the treatment period will be obtained from the prescribed dose recorded in ediary based on the date of OCS adjustments recorded in the 'Oral Corticosteroid Dose Adjustment - Treatment Phase' eCRF pages associated with each visit. If it is recorded that there was no dose adjustment for a visit, the dose of the previous visit will be considered maintained for the current visit and thus carried forward. For patients permanently discontinue treatment before Week 24/Visit 11, any dose adjustment recorded at the Early Treatment Discontinuation visit will be assigned to the regular visit after the last on treatment visit. In case there were more than one adjustments associated with one visit, the last dose will be used for the visit.

For the other efficacy assessments, the reference date for the derivation of relative days of events or findings will be the randomization day. If a patient receives IMP prior to the randomization by

Statistical Analysis Plan SAR231893-EFC13691 - dupilumab 18-May-2017 Version number: 1

mistake, the reference date of efficacy assessment will be the date of the first IMP administration for that patient. Table 9 assigns all scheduled measurements of efficacy endpoints for visits to the appropriate visit window. The ACQ-5 questionnaires planned for the weeks between visits will not be assigned to the visits. In the event of multiple measurements of the same test in the same window, the one closest to the targeted visit date will be used for the by-visit summary. If they are at the same distance to the target day, the latest one will be used.

Time windows for						
Visit	Target Day	Spirometry, ACQ-5, ACQ-7	Post-bronchodilator FEV ₁ , AQLQ(S), EQ-5D-5L, HADS, SNOT-22	Airway hyperresponsiveness (selected study sites within Canada)		
Visit 3 (Week 0)	1	-14-1 ⁻	1-	1-		
Visit 4 (Week 2)	15	1+-21				
Visit 5 (Week 4)	29	22-35				
Visit 6 (Week 6)	43	36-49				
Visit 7 (Week 8)	57	50-70				
Visit 8 (Week 12)	85	71-98	1+-126			
Visit 9 (Week 16)	113	99-126				
Visit 10 (Week 20)	141	127-154				
Visit 11 (Week 24)	169	155-182	127-210	1+		
Visit 12 (Week 28)	197	183-210				
Visit 13 (Week 32)	225	211-238				
Visit 14 (Week 36)	253	>238	>210			

Table 9 – Time window for efficacy variables

1-: up to min(1st dose date/time, end of randomization date); 1+: after min(1st dose date/time, end of randomization date).

For the pharmacokinetics/pharmacodynamics variables summary, the reference date for the derivation of relative days of measurements will be the date of first IMP administration if the patient is treated with study treatment, or the randomization date if the patient is not treated. Pharmacokinetics /pharmacodynamics variables will be summarized by the analysis window defined in Table 10 for the by visit descriptive analyses. All available values of measurements will be assigned to the appropriate visit window. In the event of multiple measurements of the same test in the same window, the one closest to the targeted visit date will be used for the by-visit summary. If they are at the same distance to the target day, the latest one will be used. For procedures planned on Visit 3, if it is done on the same date as the first IMP injection but the performance time is missing, it will belong to Visit 3 time window.

		Time windows for					
Visit	Target day	Blood eosinophil	Exhaled NO	Systemic drug concentration	Anti-drug antibodies	Eotaxin-3, total IgE, TARC Antigen- specific IgE, periostin	Sputum ILC2 and CD34 cells and sputum and blood cytokines
Visit 3 (Week 0)	1	<-1 ⁻	-14-1 ⁻	<-1 ⁻	1-	1-	1-
Visit 4 (Week 2)	15		1+-21				
Visit 5 (Week 4)	29	1+-42	22-35	1+-42		1+-56	
Visit 6 (Week 6)	43		36-49				
Visit 7 (Week 8)	57	43-70	50-70	43-70			
Visit 8 (Week 12)	85	71-98	71-98	71-126	1+-126	57-112	
Visit 9 (Week 16)	113	99-126	99-126				
Visit 10 (Week 20)	141	127-154	127-154			113-154	
Visit 11 (Week 24)	169	155-210	155-182	127-210	127-210	>154	1+-210
Visit 12 (Week 28)	197		183-210				
Visit 13 (Week 32)	225		211-238				
Visit 14 (Week 36)	253	>210	>238	>210	>210		>210
1-: up to 1 st dose date/time; 1+: after 1 st dose date/time;							

 Table 10 – Time window for pharmacokinetics/pharmacodynamics variables

For not treated but randomized patients: 1⁻: up to randomization date; 1⁺: after randomization date

